# Glossary / abbreviations

APC Admitted Patient Care

BAPRAS British Association of Plastic, Reconstructive and Aesthetic Surgeons

BOA British Orthopaedic Association

CB Commissioning brief Cl Chief Investigator

CPRD Clinical Practice Research Datalink
CTEU Clinical Trials and Evaluation Unit
EPUAP European pressure ulcer advisory panel

GP General Practitioner
HES Hospital Episode Statistics
HRQoL Health Related Quality of Life

ICD-10 International Classification of Diseases

IQR Interquartile range

ISAC Independent Scientific Advisory Committees

NHS National Health Service

NICE National Institute for Health and Care Excellence

NIHR National Institute for Health Research NRES National Research Ethics Service

ONS Office for National Statistics

OPCS Office of Population Censuses and Surveys
PICO Problem, Intervention, Comparison and Outcome

PPI Patient and Public Involvement QNI Queen's Nursing Institute

RCN DN Royal College of Nursing District Nurses

RCT Randomised controlled trial SMG Study Management Group TVN Tissue Viability Nurse

UK United Kingdom
UTS Up-To-Standard
WS Workstream

# 1. Study summary

Being immobile for too long can lead to discomfort, for example pins and needles or pain. These sensations prompt us to move and this avoids poor blood flow which can lead to pressure ulcers (sometimes called bed sores). Pressure ulcers mainly affect older people confined to a bed or chair. However, younger or seriously ill patients with limited movement, for example due to a spinal injury, can be affected.

Pressure ulcers are a serious problem for patients and their carers. They range in severity from red skin (Stage 1) to deep wounds through muscle to bone (Stage 4). Pressure ulcers have a major impact on quality of life; they may heal slowly and become infected, and can increase the risk of dying in older people. They are also a costly problem for the National Health Service (NHS). People with pressure ulcers are usually treated in the community but may need hospital care. Common treatments for pressure ulcers include pressure relief, dressings and encouraging movement and change of position. Surgery can be used to try and close deep pressure ulcers but in the United Kingdom (UK) this treatment is not common. Finding out whether surgery works as a treatment is very important to people affected by pressure ulcers. Currently, it is not clear which patients with pressure ulcers may benefit from an operation and which of the different ways of doing the surgery seems best.

The SIPS study aims to find out more about how best to conduct research in this area, by undertaking three pieces of work.

Firstly, the study will survey the opinions and experiences of doctors, nurses and patients about the range of ways in which people with deep pressure ulcers are treated. These surveys ask respondents to describe whether refer for or carry out surgery, if so, on which patients and what other treatments they use. Alongside these surveys, we will review literature about the effectiveness of surgery to treat pressure ulcers and about the impact of severe pressure ulcers on patients' health-related quality of life.

Secondly, the study will analyse data collected routinely in the NHS over a period of 8 years. The study will describe the care that has been provided in England to patients with severe pressure ulcers, the kinds of patients who have been treated in different ways and examine how care is different in different places. To inform whether surgical treatments should be more widely available, the study will identify patients who were similar when admitted to hospital with a severe pressure ulcer and compare health outcomes (such as going back to hospital and death) among those who did and did not have surgery.

Thirdly, the study will hold meetings with experienced healthcare professionals and patients to review the survey findings and the data analyses. The study will use an established method to reach agreement about which treatments are appropriate and for whom. These steps are vital to ensure relevant future research.

This study will be carried out by an experienced multi-disciplinary team of surgeons, tissue viability nurses, statisticians, researchers and patient representatives. We expect it will take two years to complete. The results will be made publicly available to inform the future care of patients with severe pressure ulcers.

# 2. Background

# 2.1 Overview of severe pressure ulcers: description, care and definition

Pressure ulcers are primarily caused by prolonged pressure on the skin, and usually effect people confined to bed or who sits in a chair or wheelchair for a long period of time. Pressure ulcers are most common on bony parts of the body, such as the heels and hips. Early symptoms include discoloured skin (stage I), but the pressure ulcer can turn into an open wound which may reach the muscle and bone (stage IV). Treatment of pressure ulcers depends on how serious they are. Initial treatments may include wound dressings, moving position regularly or specially designed cushions. However, surgical debridement can be required and in some cases surgery to remove damaged tissue and close the wound.

Studying the ways in which severe pressure ulcers are managed is challenging because the care pathway spans community- and hospital-based care. In the UK most people with or at risk of pressure ulcers are managed in the community by nurses (community nursing teams or care home staff, although some patients will receive care from a practice nurse), often with the General Practitioner (GP) acting as a conduit between community and secondary care. Since most pressure damage occurs in patients with limited mobility, most patients receive care in their own homes (which includes care homes).

Pressure ulcer prevention in at risk populations seen as a key objective in most Trusts and nurses should: undertake initial and ongoing patient-level pressure ulcer risk assessment; provide pressure ulcer prevention interventions including education and pressure relief through repositioning and the use of pressure relieving equipment; and manage existing pressure damage. When pressure ulcers occur, community-based treatment will depend on the severity of wounding. Open, superficial pressure ulcers (stage II) may be managed using dressings only but more severe pressure damage (stage III and IV) may be referred to specialist tissue viability nurses (TVNs) for advice and treatments such as negative pressure wound therapy. Despite the existence of the National Institute for Health and Care Excellence (NICE) Pressure Ulcer Care clinical guidelines, local pressure ulcer treatment pathways are heterogenous and there is variation in practice.

Tissue viability services are led by senior specialist nurses with advanced knowledge and skills, in both community and acute settings. TVNs are often responsible for the provision of advanced clinical care, the development of care pathways, and provision of education both within their own organisation and to other external organisations such as nursing homes.

The National Institute for Health Research (NIHR) put out a commissioning brief (CB) for primary research to evaluate surgical interventions for stage III and IV pressure ulcers. This brief called for a randomised controlled trial (RCT) to evaluate the effectiveness of surgical management compared to usual care for stage II and IV pressure ulcers that are not healing with conservative treatment. However, there has been little research in this area. The study team found that it was not possible to define the surgical procedures that require evaluation, the comparator group or the patient groups to be studied. A lack of information on the patient populations who currently have surgery and those who may be eligible also causes difficulties when scoping potential sites and calculating the number of potential study participants.

The study team set out to create a project which could define these unknown parameters, and so allow for an RCT to be designed in response to the CB. The first stage was to define a severe pressure ulcer. A key feature of the definition of stage III and IV pressure ulcers is that they are "full skin thickness." Some ulcers are full skin thickness but are unstageable because the features required to distinguish stage III from stage IV are not discernible. (3) These three kinds of pressure ulcer are coded as L89.2, L89.3 and L89.9 in the World Health Organisation's implementation of the International Classification of Diseases diagnosis codes version 10 (ICD-10). (4) Exploration of a sample of anonymised Hospital Episode Statistics (HES) data showed that surgical reconstruction occurred as often in patients diagnosed as having an unstageable pressure ulcer (L89.9) as in all patients diagnosed as having stage III and stage IV pressure ulcers (L89.2 and L89.3). Therefore, the study team believe that any pressure ulcer with one of these three codes is relevant to the CB.

# 2.2 Surgical reconstruction of severe pressure ulcers

Surgical reconstruction is an expensive intervention; it is potentially cost-effective providing that patients recover uneventfully and do not experience a recurrence. When studying specific patient groups who may be appropriate to undergo surgical interventions for severe pressure ulcers, as per the CB, knowledge of perceived indications for, and barriers to, surgical reconstruction are critical. Full skin thickness pressure ulcers are widely considered to represent a failure of skin care to prevent them and, therefore, understanding the circumstances in which such ulcers arise is an important aspect of the evaluation of the suitability of a patient for surgical reconstruction.

Studying surgical management of severe pressure ulcers in the UK context is challenging because surgical reconstruction is very rarely carried out. Preliminary analyses using the HES data extract obtained from the University of Bristol showed that, over two years, 81,383 patients were recorded as having had an index hospital admission in England which included an ICD-10 coded diagnosis of a severe pressure ulcer. Of these, only 165 patients also had an ICD-10 code for a reconstructive surgery during the admission.

The CB specifies that one element of the research should be an "efficient cohort study to identify priorities for future research." To do this, the study team aim to characterise the current care pathway across community and secondary care. We propose two retrospective cohort studies assembled from routine sources (HES and Clinical Practice Research Datalink (CPRD) Gold) as the most efficient cohort design. Assembling the retrospective HES cohort from routine data for England will also allow us to present data for all patients who have had their pressure ulcers managed surgically over a defined time frame, as well as understanding current practices in relevant settings.

Patients with severe pressure ulcers have restricted mobility, which may be the result of age and/or frailty, or neurological damage which limits movements. Surgery will likely only be considered in those well enough to cope, where the procedure will be successful and in those who will gain medium to longer term benefit from it. Key factors which might the influence the decision to offer surgery are life expectancy, general physical health and an agreed post-operative prevention plan which will stop a healed ulcer recurring. We were not able to find any specific data which explicitly discusses who should have reconstructive surgery. Many retrospective cohort studies are undertaken in those with spinal cord injury  but reconstructive surgery is also done in other populations and underpinning or defining features

are unclear. These observational studies do not show a differential outcome for different types of surgery but provide only very low certainty evidence.

Some small surgical case reviews have look at risk factors for postoperative complications. (7-11) Various factors were reported to be associated with post-operative complications (mainly dehiscence and recurrence), including: ulcer size, history of previous surgery, systemic biomarkers such as creatinine, chronic conditions such as coronary heart disease and body mass index (but not in all studies).

## 2.3 Uncertainties and gaps in current knowledge

There is a dearth of evidence around the evaluation of surgical interventions for stage III and IV pressure ulcers. A Cochrane review on reconstructive surgery for pressure ulcers (12) concluded that: "Currently there is no randomised evidence that supports or refutes the role of reconstructive surgery in pressure ulcer management." NICE guidance on pressure ulcers makes no recommendations about surgical management. (1) Other guidelines recommend obtaining "a surgical consultation for possible operative repair in individuals with stage III or IV pressure ulcers that are not closing with conservative treatment". (3) This recommendation does not specify specific operations or indicate the patients likely to benefit and is based on indirect evidence or expert opinion.

There is no published data from the UK describing the number of people having reconstructive surgery, and published international cohort studies look at numbers of people in a single facility (5, 13-15)

Exploration of HES Admitted Patient Care (APC) data showed that patients who had reconstructive surgery were about 20 years younger and had fewer comorbidities than those who did not. Diagnoses in addition to the pressure ulcer showed that about half had paraplegia, tetraplegia, spinal injuries or sequelae of a transport accident. These differences were also apparent between patients who had reconstructive surgery and those who had debridement only. Reconstructive surgery was carried out in 55 of 267 hospitals (20.5%) admitting index patients; in 24 months, only two performed >10 procedures and 26 did only 1. This work also found that, prior to 2012, a single ICD-10 code L89.X was used to denote any pressure ulcer.

Exploration of CPRD showed that referrals to "district nurse service" were most common (3,045 instances in 913 patients with an incident pressure ulcer). Referrals to podiatrists were second most common (682 instances in 367 patients). Referrals to TVNs were less common (286 instances in 133 patients); this was expected since such referrals are for treatment advice rather than treatment *per se*, i.e. for patients with challenging wounds.

#### 3. Rationale

The research is important because severe pressure ulcers have a significant chronicity and cause serious problems for patients, their carers and the NHS. Severe pressure ulcers have a substantial impact on Health Related Quality of Life (HRQoL) and are associated with higher care costs. The personnel and resources which are required for the ongoing effective management of these ulcers is impacting not only on NHS healthcare providers but also carers and families. The research is also important because of uncertainty about the patients in whom

reconstructive surgery to repair a pressure ulcer is effective in the short, medium and long-term, and the surgical techniques that should be used. (12) HES data show that this surgery is carried out rarely and in a minority of acute hospitals. A package of care involving surgery may be cost-effective and may need to be considered for more patients.

Several research studies have explored and quantified the additional impact of pressure-related injury on HRQoL, over and above existing health issues. A 2009 systematic review identified and synthesised 10 qualitative and 21 quantitative studies exploring the impact of pressure ulceration on HRQoL in older patients. The review identified themes which were consistently reported across studies, particularly the physical impact of ulceration (pain), psychological effects and negative impact on social activities. Additional studies including younger participants or published since the 2009 review echo these themes and reinforce the independent impact of pressure ulcers on HRQoL. One study further demonstrates that SF-36 scores in those with pressure ulcers compared with age and condition matched controls are significantly lower in terms of poorer physical functioning, role limitations due to physical problems, and vitality. Patients with complex wounds including pressure ulcers have reported that healing is the most important outcome to them. Getting rid of the wound, getting it closed and moving on, were all common sentiments in interviews with 33 such patients (8 of whom had pressure ulcers). People who had ulceration also reported, qualitatively, that healing of the ulcer did enhance HRQoL, for example by eliminating the need for bed rest and allowing a return to 'normality'. 16

This evidence shows the established link between pressure ulceration and negative HRQoL. However, there is very limited information about how surgical reconstruction impacts on HRQoL in the short, medium and long term. Surgical reconstruction of pressure ulcers is rarely carried out in the UK and the specific impact of this surgery on people with severe ulcers has not been investigated in detail. In interviews with people who had previously had ulceration, (25) small numbers of patients variously reported surgery as successful or invasive, requiring long hospital stays with ulcers recurring. Recurrence is a key issue in those at risk of ulceration, since when healing occurs the risk factors for ulceration often remain. People's access to and experience of surgery for ulceration are likely to be nested in wider issues around future prevention activity; all these aspects of care and behaviour are linked to self-reported HRQoL.

## 4. Aims and objectives

The aim of the SIPS study is to clarify the Population, Intervention, Comparator and Outcome (PICO) elements needed to be defined a future RCT of reconstructive surgery for severe pressure ulcers. We define reconstructive surgery as any surgical procedure that leads to epithelial closure of the wound, typically distant or local flaps of skin and muscle/fascia.

We have designed a study with three workstreams to address uncertainties in the "PIC" elements of a future potential PICO research question about the effectiveness and cost-effectiveness of reconstructive surgery.

Workstream 1 will include literature reviews and a survey of surgeons and nurses who manage patients with severe pressure ulcers in either secondary care or community settings.

The objectives of Workstream 1 are to:

- 1. Systematically review evidence about: (a) the effectiveness of reconstructive surgery for treating pressure ulcers; (b) the impact of pressure ulceration on HRQoL.
- 2. Carry out comprehensive on-line surveys with relevant healthcare professions to:
  - Describe the characteristics of patients in the UK currently being referred for a surgical opinion about surgical reconstruction;
  - o Describe variation in the operations and postoperative care currently being provided;
  - Describe variation in usual care provided before initiation of a surgical referral.

Workstream 2 comprises retrospective cohort studies assembled from routinely collected data sources (HES and CPRD Gold). The CPRD cohort will include data about the care pathway for patients with incident pressure ulcers, from diagnosis and management in primary care to (for a minority) secondary care and, potentially, reconstructive surgery (consultations, diagnoses, interventions and referrals both within primary care, e.g. to nursing teams, and to secondary care). The HES cohort will include information on 'index' inpatient admissions assigned an ICD-10 code for a severe pressure ulcer, and subsequent HES activity (inpatient admissions and outpatient clinic attendances).

The objectives of Workstream 2 are to:

- 3. Describe in the CPRD cohort patients with incident severe pressure ulcers and their entire care pathways, e.g. usual management in the community, management by TVNs, admission to hospital and subsequent care.
- Describe in the HES cohort patients with a diagnosis of severe pressure ulcer at the time of hospital admission, their care pathways after admission and frequencies of health outcomes.
- 5. Compare in the HES cohort outcomes in matched groups of patients who were similar on admission and who did/did not have a surgical reconstruction operation.
- 6. Explore in the matched groups subgroup interactions with reconstructive surgery that may influence outcomes, e.g. comorbidities, previous hospital admission without surgery.

[figure not shown]
Workstream 3 is a formal consensus process, separately among health professionals and patients and carers, to make recommendations about which treatments are appropriate for whom and when. The objective of Workstream 3 is to:

7. Seek consensus about which treatments and management strategies are appropriate for whom and when, given findings from workstreams 1 and 2.

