## 5.2.2.2 CPRD cohort design and target population

The request for CPRD-Gold data linked to HES and mortality data is limited to 10,000 individuals (with unlimited records per individual). Preliminary interrogation of CPRD-Gold indicated that there are ≈1,100 incident pressure ulcers (i.e. with no pressure ulcer recorded in the previous 12 months) per year recorded in CPRD, eligible for linkage to HES and mortality data. Therefore, we expect to request data for patients with an index record with a Read code

indicating an incident pressure ulcer (Table 1) during a period of eight (01/04/2011-31/03/2019) or nine years (01/04/2010-31/03/2019), subject to the limit of 10,000 individuals. All CPRD records, HES APC and outpatient episodes, and mortality data will be linked in this cohort (to 31/03/2019). The target population for the CPRD cohort is: patients >=18 years of age in England registered with a general practice with up-to-standard (UTS) registration and contributing data to CPRD, with a Read code indicating an incident pressure ulcer. No exclusions will be applied.

Table 1: Read codes to identify patients with an incident pressure ulcer

Medical code	Read code	Description
3928	M271.00	Non-pressure ulcer lower limb
4929	M270.13	Pressure sore
6862	M270.00	Decubitus (pressure) ulcer
11786	Z174P00	Pressure sore care
14995	M270.11	Bed sore
15505	39C0.00	Pressure sore
17592	39C00	Pressure sore index value
17790	Z1B3.00	Dressing of pressure sore
28380	Z9K5.00	Pressure sore prevention
28814	ZRqY.00	UK consensus classification of pressure sores 1994
35329	ZQ39.12	Pressure ulcer assessment
36995	39C4.00	Waterlow pressure sore risk score
38996	ZQ39.00	Pressure sore assessment
44641	39C1.00	Superficial pressure sore
46050	ZQ52.00	Pressure sore risk assessment
49654	ZQ39.13	Bed sore assessment
55220	ZQ39.11	Decubitus ulcer assessment
55382	39C2.00	Deep pressure sore
56610	ZRrL.00	Waterlow pressure sore risk score
63243	39C3.00	Pressure sore -deep + superfic
95113	39C6.00	Maelor pressure ulcer risk assessment score
95886	39C5.00	Medley pressure sore risk score
100638	39CA.00	EPUAP (European pressure ulcer advisory panel) grade 4 ulcer
100778	39C7.00	EPUAP (European pressure ulcer advisory panel) grade 1 ulcer
100864	39C9.00	EPUAP (European pressure ulcer advisory panel) grade 3 ulcer
101006	39C8.00	EPUAP (European pressure ulcer advisory panel) grade 2 ulcer
101713	M270200	Community hospital acquired pressure ulcer

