#### 5.2.2.6 Sample size considerations

Based on the anonymised HES extracts, HES cohort A should comprise about 120,000 index hospital admissions, including about 220 in which surgical reconstruction operations were carried out and about 3,900 in which surgical debridement without reconstruction was carried out. There are also likely to be about 170 subsequent admissions in which operations were carried out over 2 years of follow-up. Usual care for patients not having surgery will be characterised precisely.

We expect the CPRD cohort to comprise about 10,000 incident pressure ulcers. Severe pressure ulcers in the community are mainly managed conservatively; few are admitted to hospital and CPRD only covers 7% of the English population. These data will be summarised descriptively, Outcome frequencies (healing, infection, referrals to community nursing teams, TVNs and secondary care) will be estimated precisely, given this sample size. We expect to be able to follow very few incident ulcers through to surgical reconstruction.

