Patients' age, sex and comorbidities on diagnosis of a severe pressure ulcer will be described, together with details of their subsequent care in both primary and secondary care settings. We envisage that the expected, very small number of patients in the cohort having surgical reconstruction will prevent any comparisons with patients not having surgery.

5.2.3 Workstream 3: consensus groups to identify who should have surgical management and when

We will use a formal consensus method to elicit the views of health professionals and patients about which treatments and management strategies are appropriate for whom and when. Currently, we propose to use a method based on the modified nominal group technique. (40-42) The appropriateness of using this method will be reviewed as evidence from workstreams 1 and 2 emerges. We propose to recruit participants to four groups, two each of health professionals and patients. The decision to hold a separate consensus process for professionals and patients/carers is based on previous experience, which showed that it is difficult to bridge the gap relating to content knowledge and use of technical language between professionals and patients to allow a truly equitable contribution from both types of stakeholders. (43)

The consensus process will be structured to yield consensus about the primary output specified in the CB, namely identification of patient groups and interventions requiring primary research to determine effectiveness. The process will construct a set of recommendations about which treatments are appropriate for whom and when.

We will compile statements describing uncertainties about (a) the population that may benefit from an operation, (b) the operations that should be considered and (c) what should constitute usual care (range of treatment and duration before referral for a surgical opinion). These statements will be informed by the updated systematic review, survey responses of the multiple professions managing severe pressure ulcers and phenomenological interviews with patients (Workstream 1) and the findings from the retrospective cohort studies (Workstream 2).

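### Objective 3 is about incident severe pressure ulcers, but the CPRD cohort and its 10,000 are any-grade with no severe-subset rule; healing and infection are promised without being CPRD outcomes, and the 12-month look-back has no matching registration requirement

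*Protocol*

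**What the plan says.** The Protocol describes the CPRD population in two ways.

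- **Severe ulcers.** Objective 3 in section 4 is to "Describe in the CPRD cohort patients with incident severe pressure ulcers and their entire care pathways". The CPRD analysis text that closes section 5.2.2.7 says that patients' age, sex and "comorbidities on diagnosis of a severe pressure ulcer will be described".
- **Ulcers of any grade.** The Workstream 2 description in section 4 says "The CPRD cohort will include data about the care pathway for patients with incident pressure ulcers". Section 5.2.2.2 defines the target population as adults registered with an up-to-standard practice, "with a Read code indicating an incident pressure ulcer. No exclusions will be applied". The code list (Table 1) includes entries such as "EPUAP (European pressure ulcer advisory panel) grade 1 ulcer" and "Non-pressure ulcer lower limb".

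Section 5.2.2.2 treats an ulcer as incident when none was recorded in the previous 12 months. It sets no minimum time registered before the index record.

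Section 5.2.2.6 expects about 10,000 incident pressure ulcers, with no severity stated, and concludes: "Outcome frequencies (healing, infection, referrals to community nursing teams, TVNs and secondary care) will be estimated precisely, given this sample size". The CPRD outcomes in section 5.2.2.5 are Read-code frequencies, community nursing referral and discharge, tissue viability referral, hospital admission and its duration, reconstruction, and mortality.

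**The concern.** Followed as written, the plan would describe everyone with a Table 1 code and report the result against an objective about severe ulcers. Workstream 3 uses the cohort findings, with other evidence, to draft consensus statements on usual care before referral for a surgical opinion. If mild and ungraded ulcers are mixed in under a severe label, the panels may be shown a pathway that is not that of the patients a surgical trial would recruit.

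Two further gaps affect the same cohort. Section 3 reports that patients with complex wounds rate healing as the outcome that matters most, yet the promise to estimate it has no outcome definition behind it. And a patient who has just joined a practice with a long-standing ulcer has no earlier record there, so would count as incident and distort the described duration and sequence of care.

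**Working it through.** **1. Where the 10,000 comes from.** Inputs from section 5.2.2.2: about 1,100 incident ulcers of any grade a year, eight or nine years, and a cap of 10,000 individuals.

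- Nine years: 1,100 × 9 = 9,900, which is 1% below 10,000.
- Eight years: 1,100 × 8 = 8,800, which is 12% below.

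The figure reproduces on the nine-year option, and only as an any-grade count.

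**2. What Table 1 contains.** Sorting the 37 codes by description:

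| Group | Codes |
|---|---|
| Deep, or stage/grade III-IV (39C2.00, 39C3.00, 39C9.00, 39CA.00, M270600, M270700) | 6 |
| Superficial, or stage/grade I-II | 5 |
| Pressure ulcer, ungraded | 12 |
| Risk score, assessment, prevention, index or classification | 13 |
| Non-pressure ulcer | 1 |
| Total | 37 |

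Six of 37 is a share of codes. It is not a share of patients.

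**3. Precision.** The Protocol gives no interval width and no confidence level, so there is no stated precision to reproduce. Taking 95% two-sided as an assumption, the half-width is 1.96 × √(p(1 − p)/n). The Protocol does not give the severe share either, so a range is assumed.

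| Assumed severe share of 10,000 | n | Half-width, p = 50% | Half-width, p = 10% | Widening, 1/√share |
|---|---|---|---|---|
| 100% | 10,000 | 0.98 points | 0.59 | 1.0 |
| 30% | 3,000 | 1.79 | 1.07 | 1.8 |
| 10% | 1,000 | 3.10 | 1.86 | 3.2 |
| 5% | 500 | 4.38 | 2.63 | 4.5 |

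For example, at n = 1,000 and p = 50%: 1.96 × √(0.25/1,000) = 0.031. With the eight-year cohort and 10% severe (n = 880) the half-width is 3.30 points.

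**4. Healing and infection.** Section 5.2.2.6 names both as frequencies to be estimated. Section 5.2.2.5 names neither. Table 1 holds ulcer, assessment and risk codes, Table 2 referral and discharge codes, and Table 3 dressing codes. No precision can be calculated for outcomes that have no definition.

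**5. Incidence.** A 12-month look-back is informative only for someone observed for those 12 months. Section 5.2.2.2 requires up-to-standard registration but no duration, and rules out exclusions. The document gives nothing from which to size the resulting misclassification.

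**The case against.** The strongest reply is that a broad extract with severe ulcers described inside it is a legitimate design, and that the subset rule and look-back could sit in the statistical analysis plan. Part of this stands: the six codes make a severe subset possible, so objective 3 is unspecified rather than unachievable, and the registration rule is the weakest part of the point. But section 5.2.2.7 leaves only the propensity-adjusted HES analyses to that plan, severity in HES is defined by code in the Protocol itself, and Table 1 fixes who is requested.

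On healing and infection, it can be said that Read-code frequencies are an open-ended outcome and that all CPRD records are linked. That leaves room to add such codes, but none is listed.

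Three stronger readings are tempting, and the document does not support them.

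- *The promised precision fails for referrals.* Section 5.2.2.6 ties precision to ulcers of any grade and states no width. Even at 5% severe the half-width is about 4.4 points, adequate for description without a group comparison.
- *The cohort is mostly mild.* No grade distribution is given, and code counts do not supply one.
- *The remark that "few are admitted to hospital and CPRD only covers 7% of the English population" is contradicted by the HES figures.* Scaling section 2.2's 81,383 patients over two years by 7% gives 81,383 / 2 × 0.07 ≈ 2,850 a year, against 1,100 Read-coded ulcers. But the first figure counts any admission that includes a severe-ulcer code, so it takes in prevalent, hospital-acquired and incidental ulcers. The ratio does not measure how many community-managed ulcers are admitted.

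Finally, the panels also receive survey findings, so CPRD is not their only source on usual care.

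**Conclusion.** The point holds as an internal inconsistency that should be corrected. Objective 3 and the CPRD analysis text concern severe ulcers, while the cohort definition and its 10,000 concern any grade. No rule links the two, and the severe number is not stated. The precision promised for healing and infection has no defined outcome behind it. The incident definition lacks the observation time it needs.

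The loss of precision is moderate. On an assumed 10-30% severe, the half-width at p = 50% goes from about 1.0 point to 1.8-3.1 points, which is still usable. This rests on the assumed share and on 95% confidence, neither of which the Protocol gives. The larger issue is which patients the reported pathway describes. How far it would depart from the severe pathway, and how many prevalent ulcers would be counted as incident, cannot be quantified from the document.

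**What to change.** - **Severe subset.** In section 5.2.2.2, define it at index by 39C2.00, 39C3.00, 39C9.00, 39CA.00, M270600 and M270700. Report stage/grade I-II and ungraded ulcers separately, and say where the codes that do not in themselves show a pressure ulcer belong.
- **Linked HES codes, if used to establish severity.** Use the Protocol's own set from sections 2.1 and 5.2.2.1 (L89.2, L89.3, L89.9) or justify leaving out L89.9; section 2.1 reports reconstruction as often with that code as with the other two combined. Use only records at or before index, or confine this to a sensitivity analysis. Later admission is itself a CPRD outcome and must not select the cohort.
- **Sample size.** In section 5.2.2.6, give the expected number of severe cases and the resulting interval widths.
- **Incidence.** Require at least 12 months of up-to-standard registration before index.
- **Healing and infection.** Add both to section 5.2.2.5 with code lists, or delete them from the precision statement.

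The remark about few admissions need not be removed.

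The cost is definition and wording changes plus one feasibility count. The price in data is a smaller severe cohort and the loss of recently registered patients.
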